#### A3a. Financial Conflict of Interest

Does any member of study personnel (Investigator (including investigator's spouse and/or dependent children)) that are involved in the design, conduct, or reporting of the research have a Significant Financial Interest (SFI) that would reasonably appear to be affected by the research for which funding is sought and/or associated with an entity/business that would reasonably appear to be affected by the research?

No

#### A5. Funding Source:

Baylor College of Medicine (Internal Funding Only)

#### A6a. Institution(s) where work will be performed:

TCH: Texas Children's Hospital

#### A6b. Research conducted outside of the United States:

Country:  
 Facility/Institution:  
 Contact/Investigator:  
 Phone Number:

If documentation of assurances has not been sent to the Office of Research, please explain:

#### A7. Research Category:

#### A8. Therapeutic Intent

Does this trial have therapeutic intent?

Yes

### Section B: Exempt Request

#### B. Exempt From IRB Review

Not Applicable

### Section C: Background Information

The incidence of pediatric T1D in the United States is growing, with a projected prevalence of nearly 600,000 youth under age 20 diagnosed by 2050. The demanding diabetes management regimen requires constant vigilance and many complex management behaviors throughout the day and night, including frequent blood glucose monitoring, precise calculations of insulin doses, multiple insulin administrations via injections or an insulin pump, and attention to nutrition and physical activity. During adolescence, the responsibility for diabetes management begins to gradually shift from parents to youth. Declines in adherence to the diabetes regimen and in glycemic control are common, and parents and teens report increasing diabetes-related distress and family conflict during this period. Extended periods of out-of-range glycemic control raise the risk for health complications in young adulthood. Across pediatric diabetes care centers, there is a growing emphasis on preparing youth for successful transition to adult diabetes care, a primary goal of which is to equip adolescents with the skills and confidence for effective, independent self-management.

Decades of clinical diabetes research have identified contributors to suboptimal diabetes management and glycemic control in adolescence. Risk factors include depressive symptoms,  $\zeta$ diabetes burnout $\zeta$  and distress, poor health-related quality of life, diabetes-related family conflict, and parental diabetes burden. Additionally, glycemic disparities across racial and economic groups are difficult to modify and leave many youth at risk for poor outcomes. There is also a growing interest in identifying protective factors associated with good diabetes outcomes. The emerging field of  $\zeta$ Diabetes Resilience $\zeta$  focuses on adaptive behaviors that promote high quality of life, good treatment adherence, and in-range glycemic control despite the challenges and risks associated with having and managing T1D. Protective behavioral skills include effective problem-solving, adaptive coping, and constructive communication. Similarly, the ongoing involvement of parents in adolescents'  $\zeta$ diabetes management is protective, provided it is supportive, collaborative, and responsive to youths'  $\zeta$  changing developmental needs.

Empirically supported behavioral diabetes interventions include Behavioral Family Systems Therapy for Diabetes, Family Teamwork, Diabetes Coping Skills Training, and Multisystemic Therapy for Diabetes. These interventions have resulted in improved self-management skills, adherence, and glycemic control, and the involvement of parents in these interventions

highlights the central role of families in effective diabetes management in adolescence. However, the clinical impact of these interventions has been modest and benefits have been difficult to maintain. Most existing interventions aim to minimize the deleterious impact of risk factors and prevent poor diabetes outcomes by teaching new skills to address specific diabetes problems or challenges. Fewer aim to promote resilience and optimal diabetes outcomes by explicitly identifying, reinforcing, and building upon youths' and families' existing skills and strengths. Two recent behavioral diabetes interventions emphasize the positive aspects of youths' diabetes management. De Wit et al. and Viner et al. focused on issues that youth reported were currently going well in relation to their T1D. Both studies may be classified as  $\zeta$ monitoring plus feedback $\zeta$  interventions, in that youth completed questionnaires (monitoring) about positive aspects of their diabetes management (i.e., health-related quality of life, diabetes self-efficacy) and received feedback from health care providers about their responses. Improvements in quality of life and glycemic control were reported and suggest that strengths-based  $\zeta$ monitoring plus feedback $\zeta$  interventions hold potential for enhancing critical diabetes outcomes. This represents a promising next step for further development and evaluation of family-centered, resilience-oriented diabetes interventions that can complement and extend the impact of existing approaches on the clinical and behavioral outcomes of adolescents with T1D.

Limitations of traditional research interventions include that they are often time- and resource-intensive and require delivery by specialized highly trained interventionists. With rising healthcare costs and tighter margins for healthcare delivery systems, brief yet cost-effective interventions that make use of existing resources and clinical infrastructure are needed. There is increasing demand for patient- and family-centered care that focuses on value and quality, and that is accountable to both clinical and patient satisfaction outcomes. Thus, the next generation of behavioral diabetes interventions must not only improve glycemic and behavioral outcomes, but also demonstrate respect for patients and families, strengthen patient-provider relationships, and increase the value of healthcare delivery.

## Section D: Purpose and Objectives

The purpose of the current proposed study is to pilot test a newly developed strengths-based clinical intervention delivered by diabetes care providers in the context of routine ambulatory diabetes care, designed to promote resilience and support diabetes management among adolescents with T1D and their families. The emphasis of the intervention is shifting the tone of clinical encounters for diabetes care to emphasize and reinforce youths' and families' current strengths and positive diabetes management behaviors. Youth with T1D are seen routinely in clinic every 3-4 months, and this intervention will occur at two consecutive clinic visits. The intervention consists of: (A) assessing youth and family diabetes strengths and adherence prior to each visit, and (B) training diabetes care providers to tailor their clinical encounters around reinforcing each patient and family's unique  $\zeta$ diabetes strengths profile $\zeta$  generated from the strengths and adherence assessments. With its foundation in the Diabetes Resilience Model this intervention focuses on building diabetes resilience by strengthening existing protective behaviors of youth and families and by establishing supportive, patient-centered processes within the healthcare system.

The specific aims of the proposed pilot study are to: Aim 1: Assess the feasibility and acceptability of this strengths-based family intervention. Hypothesis 1A: The intervention will be feasible to conduct in the context of an ambulatory diabetes care clinic and adolescents, families, and providers will report the intervention to be highly acceptable.

Aim 2: Evaluate preliminary intervention impact on clinical outcomes, behavioral diabetes management, and patient satisfaction. Hypothesis 2A: Diabetes regimen adherence will increase and glycemic control will improve (i.e., HbA1c will decrease) from pre- to post-intervention (4-month intervention period). Hypothesis 2B: Adolescents and families will report decreased conflict, decreased diabetes burden, increased diabetes resilience, and increased satisfaction with diabetes care from pre- to post-intervention.

## Section E: Protocol Risks/Subjects

### E1. Risk Category

Category 1: Research not involving greater than minimum risk.

### E2. Subjects

Gender:

Both

Age:

Adolescent (13-17 yrs), Adult (18-64 yrs), Child (3-12 yrs)

Ethnicity:

All Ethnicities

Primary Language:

English

Groups to be recruited will include:

Patients

Which if any of the following vulnerable populations will be recruited as subjects?

Children

Vulnerable populations require special protections. How will you obtain informed consent, protect subject confidentiality, and prevent undue coercion?

Potentially eligible participants will be identified by reviewing scheduled appointments for participating diabetes care providers 6-8 weeks in advance. All patients of these providers will be screened for eligibility criteria, and potentially eligible families will be mailed an informational letter about the study. The informational letter will also include a copy of the consent form and an addressed stamped envelope for the family to return the signed consent if they choose to enroll in the study. A study phone number and email address will be provided for families to contact should they wish to opt-out of being recruited for the study. For potential participants who do not opt-out after receiving the letter, three-four weeks prior to the scheduled clinic appointment, study staff will call each family to describe the study, answer questions, and obtain informed consent. To obtain verbal consent, study staff will speak with at least one parent/legal guardian and with the adolescent. If available by telephone, a second parent/legal guardian will also be invited to participate. Families will be asked to also provide written consent on the consent form that was mailed to them, and to return it via fax, scan/email, or with the enclosed stamped envelope. Verbal consent and documentation of written consent are necessary because participants will be asked to complete questionnaires at home via web-survey prior to the study visit. If a second parent/caregiver has not provided consent or completed baseline questionnaires via web, but is present at the clinic visit, and if he/she wishes to participate, he/she will provide written consent and will have an opportunity to complete questionnaires at that time. Study staff will meet with families in a secluded and relatively private area of the waiting room, or, if available, in a private consultation room in the clinic space. The study staff member will provide the family with a duplicate copy of the consent and assent forms for their records. To protect confidentiality, a study ID number will be assigned to the participant and all subsequent data collection will be labeled with this ID number and no other identifiable information. Risks to privacy and confidentiality will be minimized through these study procedures and study staff will be trained in appropriate skills related to recruitment, obtaining informed consent, and data collection and management to avoid undue influence or coercion and to protect confidentiality.

To recruit diabetes care providers to participate, the PI will make a research presentation to the TCH Diabetes Service faculty to inform them about the study and the opportunity to volunteer to participate. Provider participation will be entirely voluntary.

### **E3. Pregnant woman/fetus**

Will pregnant women and/or fetuses (as described in 45 CFR 46 Subpart B) be enrolled in the research?

No

### **E4. Neonates**

Will neonates of uncertain viability or nonviable neonates (as described in 45 CFR 46 Subpart B) be enrolled in the research?

No

### **E5. Children**

Will children be enrolled in the research?

Yes

## **Section F: Design/Procedure**

### **F1. Design**

Select one category that most adequately describes your research:

c) Pilot

Discuss the research design including but not limited to such issues as: probability of group assignment, potential for subject to be randomized to placebo group, use of control subjects, etc.

This pilot study is a single-arm design without a control group. All participants will receive the intervention and will complete baseline and follow-up data. For the purpose of assessing intervention feasibility and acceptability, this design permits more participants to be exposed to the intervention in less time than alternative designs with a wait-list or crossover condition or control group. This will increase the ability to assess participant and provider perceptions about the intervention, to obtain valuable feedback that will help refine the intervention, and to detect any pre-post changes in study outcomes. Following pilot data collection, external funding (NIH R mechanism) will be sought to conduct a full-scale randomized controlled trial of the intervention compared to an educational, attention-control, or treatment-as-usual condition.

Inclusion Criteria:

Adolescents and families: Ninety adolescents between the ages of 12-17 years diagnosed with T1D and followed at the TCH Diabetes Care Center will be enrolled in the pilot study. At least one parent of each adolescent, self-identified as the primary caregiver most involved in diabetes care, will also be enrolled. When present, secondary caregivers involved in diabetes management will be invited (not required) to participate. Eligibility criteria will include: (1) T1D diagnosis for at least 12 months, to allow ample opportunity for adjustment to diabetes management, and (2) fluency in written and spoken English because assessment measures are not available in other languages.

Diabetes care providers: Five diabetes care providers in the TCH Diabetes Care Center (main hospital and/or satellites) will be enrolled as Resilience Promotion Providers to deliver the feedback intervention. Eligibility criteria will include: (1) Caseload of at least 20 adolescents with T1D, and (2) willing to participate in 2 training sessions, deliver the intervention to enrolled participants, and complete questionnaires.

#### Exclusion Criteria:

Adolescents and families: Presence of a serious mental illness or developmental disability in youth or parent that would impede participation would exclude eligibility.

## F2. Procedure

**BASELINE & FOLLOW-UP OUTCOME ASSESSMENTS:** Following enrollment in the study, adolescents and parents will be e-mailed a link to complete the baseline assessment battery via secure web-survey. Participants will be encouraged to complete the battery at home prior to their next clinic appointment; for anyone unable to do so, a tablet computer will be available in the waiting room before the appointment. The assessment battery administered prior to the intervention visit will also be administered at follow-up to evaluate pre-post change.

Adolescent will self-report on the frequency of 12 resilience-promoting behaviors via the Diabetes Resilience Measure for Adolescents (DRM-A). The DRM-A is a self-report assessment of positive behaviors related to diabetes resilience for youth with T1D, such as perceived competence to manage the demanding T1D regimen, to adapt to the unpredictability of diabetes, and to seek help and support with diabetes challenges. This measure requires less than 5 minutes to complete. The DRM-A will be administered in the baseline and follow-up assessment batteries, and will also be administered as part of the intervention (See below).

Parents will rate adolescents' adherence to the diabetes regimen using the 24-item Diabetes Self-Management Profile Self-Report (DSMP-SR). The version appropriate to the adolescents' current diabetes regimen (conventional or intensive insulin regimen) will be administered. The DSMP-SR was developed to be minimally burdensome compared to adherence interviews and has demonstrated satisfactory psychometric properties. The DSMP-SR will be administered in the baseline and follow-up assessment batteries, and will also be administered as part of the intervention (See below).

The following measures will be administered only as part of the baseline and follow-up assessment batteries. Adolescents will also complete the youth-report version of the DSMP-SR at baseline and follow-up to assess their perceptions of adherence. Behavioral outcomes include diabetes-related burden and family conflict. Burden will be assessed via the Problem Areas in Diabetes measures for adolescents (PAID-T) and parents (PAID-PR). The PAID-T has 26 items and the PAID-PR has 18 items, and both demonstrate good psychometric properties. Parents and youth will also complete the Diabetes Family Conflict Scale Revised (DFCS-R), a 19 item scale with good reliability and validity. To assess healthcare satisfaction, parents will complete three subscales of the Pediatric Quality of Life Inventory Healthcare Satisfaction Generic Module (PedsQL-HS), assessing their satisfaction with communication, inclusion of family, and how well the patient's emotional needs are addressed during the clinical encounter (13 items). Adolescents will rate their overall satisfaction with the patient-provider relationship on a 1-10 scale single item developed for this study, as there is no validated youth-report measure of satisfaction with care.

Clinical diabetes outcomes including glycemic control (HbA1c) and blood glucose monitoring frequency will be collected as part of routine care at each of the two study visits via blood assay and glucometer download, respectively.

**INTERVENTION:** This intervention will be delivered at two consecutive ambulatory diabetes clinic appointments (typically scheduled 3-4 months apart). Prior to each appointment, youth and parents will each complete one intervention assessment questionnaire online (DRM-A and DSMP-SR, respectively - described above). The first intervention assessment will be included within the baseline outcome assessment battery described above; for the second study visit, it will be a single survey. For each intervention assessment, the adolescent will be asked to rate specific diabetes strengths, and the parent(s) will be asked to rate behavioral adherence to various diabetes management tasks. They will also be asked to indicate one positive behavior item that they wish to discuss with their diabetes care provider. A report (referred to as Resilience Profile) will be printed for the diabetes care provider, generated from the completed intervention assessments, which will highlight the top-rated positive behaviors from each questionnaire and the positive behavior items flagged for discussion. Diabetes care providers will be trained to review the Resilience Profiles with the adolescent and family during their clinical encounter, and to provide feedback that reinforces and builds upon the positive behaviors.

At follow-up, all participating participants and providers will be asked to complete a brief survey about their experiences in the study and requesting any feedback and recommendations to improve intervention delivery or content. The provider will also be asked about their experiences with integrating the intervention into routine care, perceptions of intervention feasibility, and impact on clinic flow.

**PROVIDER TRAINING:** Five diabetes care providers who volunteer to participate in this study will be trained to provide

positive feedback to participating adolescents and families based on their unique  $\zeta$  diabetes strengths profile.  $\zeta$  Training will consist of (1) a two-hour training session with the Principal Investigator (PI) prior to participant enrollment, including instruction in the intervention protocol, demonstration, and role-play; and (2) a one-hour booster session with the PI, midway through the study period, including protocol review and role-play. The PI will also be available on an as-needed basis to answer questions and troubleshoot challenges that arise. Intervention fidelity will be assessed in two ways: (1) after each intervention visit, providers will document which components of the intervention were delivered, and (2) the PI will observe live a random sample of 10% of each provider's intervention visits with participating families.

Providers will complete a brief survey immediately following each clinical encounter with a participating family. They will be asked to rate their satisfaction with the patient-provider relationship on a 1-10 scale single item developed for this study. They will also document intervention fidelity by indicating whether and to what degree they discussed the items on the family's diabetes strengths profile.

**INCENTIVES:** To encourage completion of all outcome assessments, modest financial incentives will be offered at each data collection point. Adolescents and parents will each receive \$10 for completing the baseline and follow-up assessment batteries (\$40/family total). To encourage adolescents to bring their glucometers to the study visits, they will receive an additional \$5/visit if they bring their meter and provide it for download (\$10/family total). Parents will also receive \$12 to cover parking and transportation expenses at each of the two study visits (\$24/family total). Because the strengths questionnaires completed prior to each diabetes clinic appointment are a part of the intervention itself, no incentive will be offered for their completion so as not to coerce participant engagement in the intervention. Per family, the maximum incentive received for participation in this study will be \$74.

The participant/family will be paid for participating in this study in cash, check or with a ClinCard. Payments will be loaded onto the ClinCard within 24-48 hours of visit completion, and payment confirmations will be sent via text. The participant/family will be able to use ClinCard at any location that accepts MasterCard to make purchases and to obtain cash. During the consent process, the participant and family will be provided handouts (attached in section S) that explain how to activate and use the funds loaded on ClinCard.

To encourage diabetes care providers participate in the study, small tokens of appreciation will be given to providers in appreciation and recognition of their contributions to this research study. Providers will also be invited to co-author scholarly products that result from this research.

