When potential participants cannot be reached by telephone for study information and informed consent prior to their first clinic visit, the research coordinator will meet the family in person at the visit. At that "meet and greet" visit, the coordinator will describe the study and answer the family's questions. Consistent with the telephone procedures currently being used, this "meet & greet" process will offer families an opportunity to (a) opt-out of being recruited for the study or (b) go through the informed consent process described above. Families may then provide written consent or decline participation. Consenting families will then be enrolled in the study and will be e-mailed the link to complete the pre-intervention questionnaires online prior to their next diabetes clinic visit (e.g., 3 months later). If a second parent/caregiver has not provided consent or completed baseline questionnaires via web, but is present at the clinic visit, and if he/she wishes to participate, he/she will meet with study staff prior to the clinic appointment to learn about the study and to provide written consent and will have an opportunity to complete questionnaires at that time.

To recruit diabetes care providers to participate, the PI will make a research presentation to the TCH Diabetes Service faculty to inform them about the study and the opportunity to volunteer to participate.

For any potential participants who decline to participate in the study, research staff will invite them to share their reasons for choosing not to participate. These reasons will be documented without being linked to any personal health information, and will be reported in scholarly works resulting from this research.

Research Staff [name] is a study staff who will oversee and conduct all study activities including identifying eligible participants, preparing recruitment and study participation materials, conducting study visits, data collection, and data entry and management. [name] is a volunteer who will be helping to identify eligible participants, to prepare recruitment and study participation materials, and to assist with data management and entry. [name] is a study staff member who will assist with conducting study intervention visits, collecting data, and giving participant incentives.

Are foreign language consent forms required for this protocol?

No

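### Does the undated follow-up copy of the DRM-A and parent DSMP-SR, two scales that also feed the intervention, call for a change to the plan?

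*Combined protocol and SAP*

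**What the plan says.** F2 gives the DRM-A (adolescent) and the parent DSMP-SR two jobs, and says so for each scale. They belong to the outcome batteries: "The assessment battery administered prior to the intervention visit will also be administered at follow-up to evaluate pre-post change". They are also the intervention assessments from which the provider's Resilience Profile is produced. For visit 1 a single completion does both jobs: "The first intervention assessment will be included within the baseline outcome assessment battery described above". For visit 2 the intervention copy stands apart from the battery: "for the second study visit, it will be a single survey".

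The schedule in F2 reads: "This intervention will be delivered at two consecutive ambulatory diabetes clinic appointments (typically scheduled 3-4 months apart"). HbA1c and "blood glucose monitoring frequency will be collected as part of routine care at each of the two study visits". Hypothesis 2A in Section D covers both kinds of outcome: "Diabetes regimen adherence will increase and glycemic control will improve (i.e., HbA1c will decrease) from pre- to post-intervention (4-month intervention period").

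Baseline can be completed at several points. F2 allows a tablet in the waiting room on the day. Under E2, "three-four weeks prior to the scheduled clinic appointment, study staff will call each family to describe the study, answer questions, and obtain informed consent", and the battery can be completed at home after that. Under J2, families who consent in person at a clinic visit "will be e-mailed the link to complete the pre-intervention questionnaires online prior to their next diabetes clinic visit (e.g., 3 months later").

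G2 makes descriptive summaries of feasibility and acceptability the main analysis. Aim 2 gets a paired t-test per outcome, baseline against follow-up. G1 and G2 both say that the sample was not powered for these change analyses.

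**The concern.** A scale that is also the material of the intervention is an awkward outcome. The provider discusses and praises the answers at visit 1, the family completes the scale again before visit 2, and a later copy is then read as the result. If the follow-up copy were taken before the visit 2 encounter, change would reflect one session. If taken straight after it, change might be an immediate reaction to feedback. If the provider read it, the answers might be given with that in mind. The plan does not date that copy, and G2 does not flag the issue.

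The DRM-A is the only resilience measure described (Hypothesis 2B), and the parent DSMP-SR is one of two adherence reports (Hypothesis 2A). G1 says that trends will inform power analyses for a later randomized trial, so an unclear interval or session count would carry into that planning. Three smaller points add to the impression of looseness: HbA1c ends at visit 2 while the questionnaires may not, baseline has no earliest date, and the payment wording appears to treat the first intervention assessment as both paid and unpaid.

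**Working it through.** The plan gives no figure to reproduce on this point. The check sets the texts side by side and works out what timing they allow.

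**1. The three copies (F2)**

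| Copy | Placed | Job | Feeds a Resilience Profile? |
|---|---|---|---|
| Baseline battery | before visit 1 | outcome and intervention input | yes, the first |
| Short survey | before visit 2 | intervention input | yes, the second |
| Follow-up battery | at follow-up, no window | outcome | not stated |

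F2 builds the Profile from the intervention assessments. There are two of these, one per visit, and the follow-up battery is not one of them. Section K adds that nobody beyond the principal investigator, study staff, the IRB and the sponsor has access to identifiable research data. Providers are not expressly excluded, but the only data flow to them that the plan describes is the Profile.

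**2. Order relative to visit 2**

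Hypotheses 2A and 2B concern change from before to after the intervention, and the intervention is two visits. Before visit 2, F2 schedules only the short survey. At follow-up, participants also report on their experience of the study. A one-session reading would need the full battery to be taken before the visit 2 encounter, where F2 places something else. The consistent reading is completion after session 2. No sentence confirms it, and none contradicts it.

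**3. Interval from baseline to follow-up**

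Interval = lag from baseline to visit 1 + time between visits + lag from visit 2 to follow-up. The time between visits is taken as 3 to 4 months and the last lag as 0, the shortest case.

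| Route | Longest lag before visit 1 | Interval at that lag (months) |
|---|---|---|
| Tablet on the day | 0 | 3.0 to 4.0 |
| Telephone consent | 4 weeks = 0.92 month | 3.9 to 4.9 |
| In-person consent | 3 months | 3 + 3 = 6.0 to 4 + 3 = 7.0 |

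The extremes are 3 and 7 months, a ratio of 7/3 = 2.3. Two limits apply. The 7-month end assumes that a family completes baseline on the day of consent, which J2 does not say. The 3 to 4 months is described as typical, so it is not a bound. More to the point, the spread comes wholly from the first term. It applies equally to the burden, conflict and satisfaction scales, so it says nothing particular about the two dual-role scales or about the date of the follow-up copy.

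**4. Sessions completed before the last value**

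HbA1c and meter data: last taken at visit 2, so 1 of 2. Follow-up questionnaires: 2 of 2 on the reading in step 2. The first count follows directly from the two-visit schedule in F2.

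**5. Outcomes without the dual role**

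The youth-report DSMP-SR is in the batteries only, and HbA1c and meter-downloaded monitoring frequency are not questionnaires. Adherence therefore has comparators that never fed a Profile.

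**6. Payment**

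Batteries: 2 people × 2 occasions × $10 = $40. Meter: 2 × $5 = $10. Parking: 2 × $12 = $24. Total $74, as stated in F2 and Section L. Nothing separate is paid for the intervention questionnaires. The first of them happens to sit inside a paid battery. This is loose wording and enters no analysis.

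**The case for a change.** The strongest case for a change is that it would be cheap: a window after visit 2, a line on provider access, and a caveat in G2, with no new visit, measure or test. Saying that the sample is not powered does not tell a reader what interval was measured, and a later trial would be planned from these changes. The reading in step 2 is an inference.

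Part of this stands. The follow-up battery has no window, and the resilience outcome has no counterpart free of the dual role. But the proposed wording would leave the width of the window to the investigators, and the paired t-tests would stay as they are. It would record what analysts can report anyway from the dates on which surveys were completed. A caveat in G2 would repeat what F2 already tells the reader of the same document.

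A stronger remedy would be an extra estimate of change from baseline to the survey before visit 2. Its 95% CI half-width, t(0.975, n−1)/√n in SDs of the change score, would be 0.21 with 90 pairs, 0.24 with 72 and 0.27 with 54 (assumed completion of 100%, 80% and 60%; the plan gives no rate). Precision is not the obstacle. A gap between that estimate and the full pre-post change could not be divided between reporting conditions and the second session, so it would not answer the question.

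**Conclusion.** No change to the plan follows. What remains is a missing detail that analysts can fill sensibly: treat the follow-up battery as completed after session 2, report when it was completed, and read the visit 2 HbA1c and meter values as following one session. The dual role is a disclosed feature of a monitoring-plus-feedback intervention. The payment wording is a clerical matter.

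No size or direction of bias is established. The 3 to 7 month range is an outer limit under the assumptions shown, and it is common to all questionnaires. Any effect is confined to the interpretation of two secondary, exploratory outcomes in a single-arm pilot, where pre-post change could not be credited to the intervention in any case. The Aim 1 summaries do not use these scores.

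The conclusion rests on two assumptions: that the wording in Section D and F2 means what it most naturally says about order and provider access, and that completion dates are kept. If the full battery were in fact taken before the visit 2 encounter, change on every follow-up questionnaire would cover one session and should be described that way. The paired analysis itself would be unaffected.
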